5.11 Tools to be used

A form will be used to collect demographic data and the variables to be studied (Annex 1).

6 Ethical considerations

This protocol will be submitted for review and evaluation by the Research Ethics Committee in each of the participating institutions to obtain the respective approval for its execution.

The study is by the provisions of Resolution 8430 of 1993 of the Colombian Ministry of Health, according to article 11 numeral b, is classified as minimal risk, given that data records were used through common procedures consisting of a sample collection (blood) by capillary puncture. In addition, the criterion of respect for the dignity and protection of the rights and welfare of the participants will prevail.

Informed consent will be requested in written form to all participants, giving clear and easily understandable information about the objectives of the research. The consent will be explained and doubts about it will be resolved, and complete freedom will be given to withdraw consent at any time during the study, for the reasons that the subject considers (Annex 2).

The study will be coordinated by health professionals and the sampling and data collection will be performed by trained nursing assistants. The confidentiality of the data collected will be guaranteed, the information obtained will not be used for purposes other than the current research process, and at the time of disclosure of the information, sensitive data or data that allow the identification of the participating individuals will not be published, the rules outlined in the law 1581 of 2012 on habeas data will be followed.

None of the authors have conflicts of interest to declare.

7 Expected results & impact

Strengthening of the scientific community

Expected Result/Outcome	Indicator	Beneficiary
Screening adults with risk factors for hepatitis C	The proportion of people diagnosed with hepatitis C	Users affiliated with the SGSSS, benefit plan administrators, and health personnel.
Linkage to treatment of confirmed positive cases for HCV infection in the hospitals included in the study.	The proportion of people diagnosed with chronic hepatitis C who started treatment	Users affiliated with the SGSSS, benefit plan administrators, and health personnel.

Social appropriation of knowledge

Expected Result/Output	Indicator	Beneficiary
Circulation of specialized knowledge: Presentation of results in scientific events (national and international).	Participation in scientific events presenting research results.	Medical-scientific community, decision makers, hospital institutions.
Circulation of specialized knowledge: Presentation of results to stakeholders of the Colombian SSSSS.	Participation in events with different stakeholders of the USGS.	Insurers and providers of the SGSSS, patients at the national level.

Generation of new knowledge

Expected Result/Output	Indicator	Beneficiary
Research article submitted to a journal indexed in one of the bibliographic citation indexes such as ISI-Web of Knowledge (Science Citation Index (Raffone et al.) and Social Sciences Citation Index [SSCI]) or SCOPUS, Publindex, Lilacs, BVS, Latindex, among others.	Scientific articles published.	Medical-scientific community, decision makers, hospital institutions.

Expected impacts from the use of results

Expected Impact	Time (years) after completion of project* 1-4 years	Verifiable indicator	Assumptions
Improved timeliness of detection of new cases of hepatitis C in the hospital setting.	1-4 years	Increase in incidence rate for hepatitis C	Medical staff adhering to the screening and diagnostic algorithm - applicability of the algorithm in people with risk conditions and exposures.
Improved time between confirmatory PCR diagnosis and initiation of treatment.	1-4 years	Increase in the number of persons diagnosed with chronic hepatitis C who initiated treatment	Standardization of route that allows compliance with all stages for the diagnosis, treatment, and follow-up of the patient with CH.
Successful completion of treatment	1-4 years	Increase in the proportion of patients with cure (sustained viral response)	Timeliness of follow-up, patient adherence to treatment regimen.
Changes in chronic hepatitis C prevalence figures	5-9	Trend in the crude prevalence of chronic hepatitis C	Timely detection and treatment cause a decrease in the risk of transmission.

Short (1-4), medium (5-9), long (10 or more)

8 Communication strategies

Each institution will use its mechanisms for the dissemination of the project and participatory strategies that it determines appropriate according to the type of clinical research and its institutional policies after consultation with the Colombian Association of Hepatology.

9 Trajectory of the researchers participating in the research project

performed in the laboratory of the same institution at the cost of the project at a rate of COP 238,000 (USD 49,96) for each viral load if the institutional laboratory expresses interest in processing the viral load samples of the cases with positive antibodies and after signing an agreement.

Leadership in the communication and management of project resources vis-à-vis healthcare institutions is provided by the ACH, its board of directors, and the acting president or designee, along with alignment with each participating project institution leader.

ACH is the author of the project and will provide the resources for the execution of the project. The items covered in the execution of the study do not include the costs of treatment or any clinical management procedure (for example, visits to the doctor, or follow-up laboratories) since they are part of the usual treatment for hepatitis C virus infection and it is contemplated in the Colombian regulations that once the case of confirmed hepatitis C is notified to SIVIGILA (file 340), every quarter the High Cost Account downloads that information, includes the patient in the national cohort of high-cost diseases-Hepatitis C, establishes communication/audit with the Benefit Plan Management Company (EAPB) to which the patient belongs and guarantees their linkage to treatment, treatment against hepatitis C which is free, at no cost to the EAPB or out-of-pocket expense for the patient and which is acquired in annual purchases by the CAC since 2017 through the centralized purchasing mechanism from the Pan American Health Organization.

12 Annexes

12.1 Annex 1. Data collection instrument

Adult screening for hepatitis C and linkage to treatment in Colombian hospitals	
Patient's name:	Identification number:
Age (in years):	Sex: Male: ___ Female: ___
Contact phone number:	Residence address: Department of Residence: Municipality of residence:
Affiliation scheme: 0. Uninsured: _____ 1. Subsidized: _____ 2. Contributory: _____ 3. Special: _____ 4. Exception: _____	Institución prestadora de servicio de salud (IPS): Fundación cardiointantil _____ Fundación Santafé _____ Clínica Colombia _____ Hospital Universitario San Ignacio _____ Fundación Valle de Lili _____ Hospital Pablo Tobón Uribe _____ Hospital Universitario Julio Méndez Barreneche E.S.E. _____
E-mail: _____ Nationality: _____	
Received blood transfusion before 1996: YES ___ NO ___	Year of transfusion:
Name of EAPB or Entity obliged to compensate:	Major Surgery: Yes ___ No ___ Type of surgery: Abdominal laparotomy: Yes ___ No ___ Gynecologic surgery of any type: Yes ___ No ___ Orthopedic surgery of any type: Yes ___ No ___ Any surgery that has required post-procedure in-hospital surveillance: Yes ___ No ___
Tattoos: Yes ___ No ___	Intravenous drug user: Yes ___ No ___ Nasal drug user: Yes ___ No ___
Man who has sex with men: Yes ___ No ___	Known hepatitis B virus infection: Yes ___ No ___
Known HIV infection: Yes ___ No ___	Have you ever had tattoos or body piercings? Yes ___ No ___
Abnormal liver tests or with liver disease:	Healthcare workers or members of public

Yes__ No__	safety (e.g., correctional service officers or police) who have come into contact with blood at work through needle sticks or sharps injuries: Yes__ No__
A person who has undergone hemodialysis: YES__ NO__	Diagnosis of diabetes: YES__ NO__
Diagnosis of Cryoglobulinemia: YES__ NO__	Diagnosis of coronary artery disease: YES__ NO__
Diagnosis of renal failure: YES__ NO__	
Population deprived of liberty or previously incarcerated persons: YES __NO__	
HCV antibody detection test: Non-reactive: _____ Reactive: _____	
Viral load test: Positive: _____ Negative: _____ Not applicable: _____(in all cases where HCV antibody screening test is non-reactive).	
Case reported to Sivigila YES__ NO__	
The positive case has been followed up YES __NO__	
The patient has had access to a specialized consultation YES __NO__ Why?	
The patient was able to access treatment YES __NO__ Why?	
Date of completion:	
Name of the person doing the diligence:	

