5.3 Inclusion criteria

Have at least one of the following risk factors for hepatitis C.

- Over 50 years of age with no risk factors.
- Over 18 years old and < 50 years old, with risk factors for hepatitis C:
 - ✓ Persons who have received medical or dental interventions in health care settings.
 - ✓ Persons who have had tattoos, body piercings, or scarification procedures.
 - ✓ Persons with HIV or hepatitis B infection.
 - ✓ Persons who inject drugs.
 - ✓ Persons who have used intranasal drugs.
 - ✓ Persons deprived of liberty and previously incarcerated persons.
 - ✓ Anyone with abnormal liver tests or liver disease.
 - ✓ Students, health care workers, or members of public safety (e.g. correctional

service officers or police) who have come into contact with blood at work through needlestick or sharps injuries.

- ✓ Anyone who has undergone hemodialysis.
- ✓ Persons who received transfusions in Colombia before 1996.
- ✓ Persons with comorbidities potentially associated with CH: diabetes, ischemic heart disease, cryoglobulinemia, chronic renal failure, Sjögren's syndrome, hypothyroidism, lichen planus, rheumatoid arthritis, HIV, non-Hodgkin's lymphoma, acute lymphoblastic leukemia, waldenstrom's macroglobulinemia.
- Individuals previously treated for HCV with sustained viral response in whom reinfection is suspected (individuals who continue to engage in risk behaviors)
- Accept to participate in the study by signing the informed consent form.

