	Inhaled or intranasal drug use	Having consumed inhaled drugs at any time.	0. No 1. Yes	Nominal, dichotomous
	Men who have sex with men	Man who has had sex with men.	0. No 1. Yes	Nominal, dichotomous
	Known hepatitis B virus infection	Refer to have a diagnosis of hepatitis B virus.	0. No 1. Yes	Nominal, dichotomous
	Known HIV infection	Refer to HIV diagnosis.	0. No 1. Yes	Nominal, dichotomous
	People who have had tattoos, body piercings, scarification, etc.	Presence of tattoos or piercing or scarification.	0. No 1. Yes	Nominal, dichotomous
	Population deprived of liberty or previously incarcerated persons	Being or having been deprived of liberty in a penitentiary center.	0. No 1. Yes	Nominal, dichotomous
	Liver disorders or disease	A person with abnormal liver	0. No 1. Yes	Nominal, dichotomous

Category	Variable name	Conceptual definition	Operational definition	Measuring scale
		tests or liver disease.		
	Occupational exposure	Healthcare workers or members of public safety (e.g., correctional service officers or police) who have been in contact with blood at work through needlestick or sharps injuries.	0. No 1. Yes	Nominal, dichotomous
	Hemodialysis	A person who has undergone hemodialysis.	0. No 1. Yes	Nominal, dichotomous
	Comorbidities potentially associated with HCV infection.	Diabetes, Ischemic heart disease, Cryoglobulinemia, Chronic renal failure, Sjögren's syndrome, Hypothyroidism, Flat lichen, Rheumatoid arthritis, Non-Hodgkin's lymphoma, Acute lymphoblastic leukemia, Waldenstrom's macroglobulinemia, Chronic renal insufficiency, Sjögren's syndrome	0. No 1. Yes	Nominal, dichotomous
Missed opportunity	Doctor visits	Doctor visits in the last month	How many?	Continued
Sample results	HCV antibody screening test	Report of HCV antibody test result.	0. Non-reactive 1. Reactive	Nominal, dichotomous
	Viral load test	Report the viral load result of those patients who presented reactive HCV antibodies.	0. Non-reactive 1. Reactive	Nominal, dichotomous

Category	Variable name	Conceptual definition	Operational definition	Measuring scale
Follow-up	SIVIGILA Report	The confirmed cases of HCV as a public health event are reported to the surveillance system utilizing form 340.	0: Not reported 1: If reported	Nominal, dichotomous
	Follow-up of confirmed case	Follow-up that each case confirmed in the study has access to consultation by a clinical specialist.	0. No Why? 1. Yes	Nominal, dichotomous

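### The form's renal item is broader than the definition in 5.3 and 5.5, and the occupational item omits students whom 5.3 admits, so some risk-factor records can be misclassified

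*Combined protocol and SAP*

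**What the plan says.** **Renal item.** Section 5.3 lists, among the comorbidities that qualify a person, "diabetes, ischemic heart disease, cryoglobulinemia, chronic renal failure". The variables table in 5.5 opens its list with "Diabetes, Ischemic heart disease, Cryoglobulinemia, Chronic renal failure" and later adds "Chronic renal insufficiency", so every renal term in the two definitions carries the word chronic. In 5.5 this is not a separate variable. It is one component of a single yes/no comorbidity variable. The form in 12.1 (Annex 1) asks "Diagnosis of renal failure: YES__ NO", without the word chronic.

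**Occupational item.** Section 5.3 admits "Students, health care workers, or members of public safety" who have had contact with blood at work through needlestick or sharps injury. The variables table defines the matching variable as "Healthcare workers or members of public safety (e.g., correctional service officers or police) who have been in contact with blood at work". Annex 1 names the same two groups as the variables table. Students appear in neither.

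**Use.** Section 5.10 describes all variables with frequencies and percentages, and explores risk factors against positive antibodies with chi-square tests.

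**The concern.** A form should record the variable that the plan defines. Here two items do not.

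- **Renal.** Sections 5.2 and 5.6 include hospitalised and emergency patients, among whom acute renal failure can be expected. Such a patient answers the printed question truthfully with Yes. Nursing assistants collect the data (section 6), and Annex 1 carries no definition that would settle the point. The result would be people without the chronic condition in the exposed group, which dilutes any association.
- **Students.** Annex 1 has no field for the inclusion criterion met. A student under 50 whose only qualifying ground is a sharps injury may therefore leave a form with no risk factor on it. The count of occupational exposure is then too low, and eligibility cannot be confirmed from the record.

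The weekly data review in 5.9 is unlikely to catch either case, because a literal answer to the printed question does not look wrong. Section 12.2 lists an edit command for users only and allows no deletion, so it is better to correct the wording early.

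**Working it through.** **Step 1. The texts side by side**

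| Item | 5.3 | 5.5 variables table | Annex 1 |
|---|---|---|---|
| Renal | chronic | chronic | not restricted to chronic |
| Students, occupational exposure | named | not named | not named |

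The renal mismatch lies between the form and both definitions. The student mismatch lies between 5.3 on one side and the variables table and form on the other; those two agree with each other.

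**Step 2. What is not affected**

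The sample size in 5.8 uses p = 0.5, d = 0.05, a design effect of 3 and N = 280,186. With z = 1.96, n = 3Np(1−p) / [(d²/z²)(N−1) + p(1−p)] = 1,150.86, which reproduces the stated 1,151. No risk-factor variable enters it. The prevalence estimate rests on the test results and does not use these two items.

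**Step 3. Illustration, renal item**

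The documents give neither the share with acute-only failure nor the strength of any association. Assumptions: positivity r0 = 1% in the unexposed, true odds ratio 3, and acute-only patients carry the unexposed risk. The exposed odds are then 3 × 0.01/0.99 = 0.030303, so r1 = 0.029412. Let e be the share of participants with chronic failure and a the share with acute-only failure.

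- Share of Yes answers that are not chronic = a/(e + a)
- Positivity among Yes = (e·r1 + a·r0)/(e + a); positivity among No stays at r0

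With e = 0.05 and a = 0.05, half of the Yes answers are not chronic. Positivity among Yes is 0.019706, and the odds ratio is 0.020102/0.010101 = 1.99. With e = 0.10 and a = 0.01, the non-chronic share is 9.1% and the odds ratio is 2.81. Over e of 5% to 10% and a of 1% to 5%, the odds ratio runs from about 2.0 to 2.8.

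That is for the renal field alone. The 5.5 variable is the composite, and it changes only for people with no other listed comorbidity. Suppose 20% to 30% are truly exposed, every true case is captured, and r0 = 0.67% (the modelled national prevalence in the introduction). The odds ratio is then:

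| Acute-only share among the rest | Composite odds ratio |
|---|---|
| 0.5% to 1% | 2.92 to 2.98 |
| 2% | 2.85 to 2.91 |
| 5% | 2.66 to 2.79 |
| 10% | 2.42 to 2.62 |

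**Step 4. Illustration, students**

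Keep r0 = 1% and a true odds ratio of 3. Let e be the share truly exposed and s the share of those who are students recorded as No.

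- Recorded frequency = e(1 − s)
- Positivity among No = (e·s·r1 + (1 − e)·r0)/(e·s + 1 − e)

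With e = 0.02 and s = 0.3, the recorded frequency is 1.4% instead of 2.0%. Positivity among No is 0.010118, and the odds ratio is 0.030303/0.010221 = 2.96. With s = 0.1 the figures are 1.8% and 2.99. At the extreme tried, e = 0.05 and s = 0.5, the odds ratio is 2.86.

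**The case against.** A reader might infer that both variables are miscoded whenever the form is completed as written. The documents do not support that.

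- Renal failure includes chronic renal failure, so every true chronic case is still recorded as Yes.
- The occupational item on the form agrees with its definition in 5.5. Only the match to 5.3 fails, and only for students whom staff do not already count as healthcare workers.
- A person under 50 with acute renal failure enters only if some criterion in 5.3 is met, so the under-50s who could be miscoded on the composite are those admitted on another ground. People over 50 need no risk factor.

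The composite figures above are also optimistic about the form. Annex 1 has diagnosis fields for only four of the eleven distinct comorbidities in 5.5: diabetes, cryoglobulinemia, coronary disease and renal failure. If that lowers capture to an assumed 80%, with 20% exposed, the odds ratio is already 2.74 with no acute-only cases and becomes 2.57 with 2%. The missing fields can therefore matter more than the missing word.

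Further, the acute-only shares have no source in the documents, outpatients are recruited too, 5.10 plans chi-square tests and no odds ratios, and renal failure alone is not a variable in 5.5. The word chronic may have been lost in translation, which the documents cannot settle.

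All of this limits the size of the effect. It does not remove the two differences in wording, and nothing elsewhere in the plan resolves them.

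**Conclusion.** The point holds as a minor inconsistency between the definitions and the form. Some participants with acute-only renal failure can be coded as having a listed comorbidity, and some students with sharps exposure can be coded as unexposed.

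The renal part can weaken an association in the exploratory analysis. The student part barely moves the association: under 2% of the odds ratio when 2% are exposed and 10% to 30% of those are students, and just under 5% at the extreme tried. Its main effect is on the exposure count and on whether the ground for entry can be seen in the record.

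The odds ratios are illustrations that rest on assumed shares, an assumed true odds ratio of 3 and acute-only patients having the unexposed risk. They are not predictions for this study. A reader might also infer that the main result is biased; it is not, because prevalence and sample size do not depend on these items.

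**What to change.** Align the wording with the protocol's own text:

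1. In Annex 1, change the renal field to *Diagnosis of chronic renal failure*, matching 5.3 and 5.5.
2. In the variables table (5.5) and in Annex 1, begin the occupational item with "Students, health care workers, or members of public safety", as in 5.3.
3. Carry both changes into the electronic form going forward. The completion date on the form lets records before and after the change be told apart.

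The cost is two wording changes on the form and one in the variables table, plus whatever notice of a revised form the institutions' ethics committees require. No extra participants or tests are needed.

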12.2 Annex 2. Information security for web applications in Hostinger with MySQL

Information security is a critical priority in the development and operation of web, mobile, and desktop applications. This section aims to provide an overview of best practices and security measures implemented and best practices to be performed during project execution to protect sensitive information and ensure the availability and integrity of the application.

I. Authentication and Authorization

1. Application access password: Secure and complex passwords must be used. The use of combinations of upper- and lower-case letters, numbers, and special characters is recommended. The password will be assigned directly at the time of user creation.
2. Two-factor authentication (2FA): Implement two-factor authentication to add a layer of security to application and database access. Two-factor authentication will work for access

to Hostinger, where the VPS server administration, MySQL database, and web hosting configuration are located.

3. Role-based authorization for Hostinger: Establish appropriate roles and permissions to ensure access to the dashboard and administration of the server, hosting, and database of the project. The administration will be in charge of Crececos - Laboratorio de Estrategias Digitales SAS, a strategic ally for the digital management of the Association, working on management issues, updates, software patches, and product updates. Access and permissions to additional users will be requested and established by the Colombian Association of Hepatology.

4. Role-based authorization for the application: Establish appropriate roles and permissions to ensure that users only have access to the parts of the application according to their responsibility. Three roles were defined with the following permissions:

a. SUPER ADMINISTRATOR: Will have full access to the web application where he/she can manage users, full access to the dashboard and download information, quick test upload, and viral test upload.

b. ADMINISTRATOR: Will have partial access to the web application where he/she will have access to the dashboard filtered by the medical institution to which he/she belongs and will be able to download the corresponding information, upload quick tests, and upload viral tests.

c. OPERATIVE: Will have partial access to the web application where he/she will be able to access the dashboard filtered by the medical institution to which he/she belongs, upload the rapid test, and upload the viral test.

5. Authorization and remote access to the database: Direct access to the database through some database viewer or terminal, you will have to access with user credentials, and password and have SSH authentication, which will be managed by Hostinger administrator staff. It is recommended not to access directly to the database in this way.

II. Data Protection

1. Data Encryption: HTTPS (SSL/TLS) implementation to encrypt the communication between the client and the server. Also, a proprietary API was implemented to channel communications with the database, and the storage of confidential information was configured especially for sensitive information:

- a. Auto incremental and auto-generated ID for records in the database.
- b. Relation of the information employing IDs specific to each record.
- c. Patient's ID only for linking rapid load test with viral load test.
- d. Confidentiality of the patient's name in the database storage.

2. API Implementation: Development and implementation of a proprietary API Rest (backend) to channel and control direct communications with the database. The API has access to the database in secret and encrypted files inside the same server.

Authentication and authorization middlewares were implemented for user access and a layer of DTOs (Data Transfer Object) was implemented to validate the information that the API receives and responds to the capture web application (client). The connection to the private API is made by the capture web application (client) using its encrypted keys. The communication protocols allowed by the API:

- a. GET: Get information, download information
- b. POST: Upload quick test form, upload viral upload form, and user creation.
- c. PUT Edit users
- d. DELETE: No delete commands are allowed.

III. Updates and Patches

1. Keep Software Updated: Keep the operating system, the web server, the MySQL database, and all libraries and frameworks used updated with the latest security patches.
2. Audit Code: Perform regular security audits of application code to identify potential vulnerabilities and correct them promptly.

IV. Attack Protection

Firewalls and Security Filters: Configuration of firewalls and security filters to block malicious traffic and common attacks, such as brute force attacks and SQL injection. Hostinger features DDoS protection and a configurable firewall for SSH and HTTP protocols and port definition.

Security Monitoring: Periodic security monitoring to detect unusual or potentially malicious activity and generate alerts.

V. Backup and Recovery

1. Backups: Scheduling regular backups of the MySQL database and application files.

Storage of these copies in secure locations. Full server backups perform automated snapshots every week and even the possibility of generating manual snapshots on demand or application updates. In case of any vulnerability or inconvenience, it is possible to revert to a previous version quickly.

2. Business Continuity Plan: In case of any security incident, access vulnerability, or even server downtime, the following recovery and business continuity procedures are in place:

- a. Backups and copies of the databases in a server outside Hostinger.
- b. Repositories of the capture web application (Frontend) and the API (Backend) in Github for rapid deployment on a different server.
- c. No dependency on a specific server to be able to deploy and run the application again.
- d. Restoration of the latest database backup version.

VI. Education and Awareness

User and staff training: Educate Users Association staff and project participants from each medical institution about security practices, the importance of strong passwords, and how to recognize phishing attacks and other fraud attempts.

VII. Legal Compliance

Regulatory Compliance: Hostinger has data centers located in North America, Europe, Asia, and South America. Each server used for hosting web pages, web applications, and other services has encryption and information security certifications. Additionally, the aforementioned document is defined with the architecture and security protocols as requested in the acceptance criteria of the capture web application.

Conclusion

Information security is an ongoing and constantly evolving endeavor. This document provides a foundation for ensuring the security of a web application hosted by Hostinger with a MySQL database, but it is essential to continue to monitor and update security measures as the security threat evolves.

